3.6 Secondary endpoints

3.6.1 Confirmatory secondary endpoints

All confirmatory secondary endpoints will be presented and analysed using FAS, unless otherwise specified.

The primary analysis for the confirmatory secondary endpoints is the pattern mixture model using multiple imputation and using all available data, including data collected after treatment discontinuation and initiation of rescue medication. The model is described in detail in the primary analysis for the primary endpoint, except that the baseline value of the analysed endpoint will be included instead of the baseline HbA_{1c} . value For the dichotomous endpoint (HbA_{1c} <7.0%), a

Liraglutide Trial ID: NN2211-3659	CONFIDENTIAL	Date: Version:	2.0	Novo Nordisk
Statistical Analysis Plan EurdraCT No.: 2011-002605-29		Status: Page:	Final 16 of 25	ı

logistic regression model will be used with missing values imputed from the pattern mixture model of change from baseline in HbA_{1c}

In addition, the confirmatory secondary endpoints will be analysed by an MMRM model using all data points for all visits, but excluding data collected after treatment discontinuation or initiation of rescue medication. Fixed factors in the model are treatment and stratification groups (gender*age group), with baseline value of the analysed endpoint included as covariate., Both fixed factors and the covariate will be nested within visit (sensitivity analysis no. 4 for the primary endpoint). For measurements within a subject an unstructured covariance will be used. For the dichotomous endpoint (HbA_{1c}<7.0%), a logistic regression model will be used with missing values imputed from the corresponding MMRM model of change from baseline in HbA_{1c}.

The continues confirmatory endpoints will be presented as described for the primary analysis.

Change from baseline in FPG after 26 weeks of treatment

The change from baseline in FPG after 26 weeks of treatment will be analysed with the same method as the primary efficacy endpoint (as described above). Baseline FPG will be included in the analyses instead of baseline HbA_{1c} .

$HbA_{1c} < 7.0\%$ after 26 weeks of treatment (yes/no)

This dichotomous endpoint will be analysed by a logistic regression model. Effects in the model are treatment, stratification groups (gender*age group), and baseline HbA_{1c} as a covariate. The results will include the 95% confidence interval for the odds ratio (liraglutide over liraglutide placebo) and the p-value for test of no difference between the groups as part of the presentation. Missing data for HbA_{1c} at week 26 will be imputed from the multiple imputation procedure of the primary endpoint (as described above).

Change from baseline in BMI SDS after 26 weeks of treatment

The change from baseline in BMI SDS after 26 weeks of treatment will be analysed with the same method as the primary efficacy endpoint (as described above). Baseline BMI SDS will be included in the analyses instead of baseline HbA_{1c}.

BMI SDS will be calculated using the following formula:

$$Z = \frac{\left(\frac{measurement}{M}\right)^{L} - 1}{S * L}$$

where L,M and S are median (M), skewness (L) and variation coefficient (S) of children's BMI provided for each sex and age . For each subject a standard deviation score Z (SDS) will be calculated based on age and sex referring to the values L, M and S. The method is described in the WHO Multicentre Growth Reference (3) Values for M, L and S by age and sex is also found in the WHO reference. For Z (SDS) scores below -3 and above 3 the score will be adjusted as described in the WHO instruction.

Liraglutide
Trial ID: NN2211-3659
Statistical Analysis Plan
EurdraCT No.: 2011-002605-29

Date: 25 June 2018 Version: 2.0
Status: Final
Page: 17 of 25

Hierarchical testing

The primary endpoint and confirmatory secondary endpoints will be analysed in a hierarchical manner in the following order:

- 1. Primary efficacy endpoint
- 2. Change from baseline in FPG after 26 weeks of treatment
- 3. $HbA_{1c} < 7.0\%$ after 26 weeks of treatment (yes/no)
- 4. Change from baseline in BMI SDS after 26 weeks of treatment

In order to be able to conclude significance for an endpoint in the hierarchical list above, the test for that endpoint and the tests for the endpoints higher up in the hierarchy must all be concluded significant with a difference in favour of the liraglutide group.

The hierarchical testing is chosen to maintain the family wise type I error of 5%.

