8.1.5 Visits

Procedures for the scheduled site visits and phone contacts are described in the following section and in the flow chart (please refer to section [2](#)). In order to secure consistency in data over time it is encouraged that assessments are performed consistently (e.g. using the same type of equipment and trial site staffs with alike qualifications) during the trial.

For visit numbers, timing of site visits, phone contacts and visit windows during the trial period, please refer to the flow chart (section [2](#)). It is the responsibility of the investigator to ensure that all site visits and phone contacts occur according to the flowchart. A phone contact may be converted to a site visit, if needed.

There will be one follow-up visit (Visit 26) for all subjects. Subjects treated with liraglutide for more than 3 months should in addition attend a 1 and 2 year follow-up visit (Visits 27 and 28). There will be no diaries attached to these visits and hence reporting of AEs and SAEs will be by the subject's and subject's LAR's memory.

Visits attended fasting

Subjects must attend the clinic in a fasting state for Visits 1, 7, 13, 17, 22 and 25 blood sampling. Fasting is defined as at least eight hours without food or drink intake except for water and prescribed medication other than diabetes medication.

In addition subjects must be without food or drink intake except for water and prescribed medication for at least 2 hours before Visit 26 blood sampling.

Should a subject attend a fasting blood sampling in a non-fasting state blood sampling must be re-scheduled, preferably within the visit window.

Unscheduled and missed visits

If a subject attends the clinic for an unscheduled visit, the unscheduled visit form must be completed unless the subject attends the clinic to obtain additional IMP, NIMP, auxiliary supplies or to perform a re-test of a blood sample. If the subject needs additional IMP and/or NIMP an additional dispensing call should be made in the IV/WRS.

Should a visit be missed, every effort should be made to re-schedule the visit within the allowed visit window. If this is not possible the visit should be re-scheduled at the earliest possible date.

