8.6 Assessments for efficacy

8.6.1 Body measurements

Body measurements consist of the following parameters:

- Body weight (Visits 1, 7, 11, 12, 13, 15, 17, 18, 20, 22, 24, 25, 27 and 28)
- Height (safety endpoint) (Visits 1, 7, 13, 17, 25, 27 and 28)
- BMI (calculated at Visit 1)
- Waist circumference (Visits 1, 7, 13, 17 and 25)

Body weight

Body weight should be measured (kilogram or pound [kg or lb], one decimal) without shoes and only wearing light clothing. Preferably the same set of scales should be used throughout the trial.

Height

Height should be measured (centimetres or inches, one decimal) without shoes as two individual measurements performed by a single observer using identical technique with a Harpenden or other wall mounted stadiometer. The subject should be repositioned between the two measurements.

Waist circumference

The waist circumference is defined as the minimal abdominal circumferences located midway between the lower rib margin and the iliac crest.

Three consecutive measurements of waist circumference should be taken and recorded in the eCRF. The waist circumferences will be measured to the nearest 0.5 cm (0.2 inches) using a non-stretchable measuring tape.

The subject should be measured in a standing position with an empty bladder and wearing light clothing with accessible waist. The subject should be standing with arms down their side and feet together. The tape should touch the skin, but not compress soft tissue and twist in tape should be avoided. The subjects should be asked to breathe normally and the measurement should be taken when the subject is breathing out gently.

BMI

The BMI will be calculated by the eCRF based on the height and weight as described above. At the screening visit the investigator must verify subject's eligibility for the trial according to the BMI inclusion criteria see section [6.2](#) and Appendix A.

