3.5 Primary endpoint

The primary endpoint is change from baseline to week 26 in HbA_{1c}. The FAS will be used for this analysis. All available data will be used, including data collected after treatment discontinuation and rescue initiation. A pattern mixture model using multiple imputation will be used.

The null hypothesis is no difference between the changes from baseline in HbA_{1c} (%) after 26 weeks of randomised treatment with liraglutide + metformin with or without basal insulin and liraglutide placebo + metformin with or without basal insulin (H0: d= liraglutide – placebo =0). The alternative hypothesis is that there is a difference between the two treatment arms (HA: d \neq 0). Superiority of liraglutide over liraglutide placebo will be concluded if the 95% confidence interval for the treatment difference for change from baseline in HbA_{1c} (%) after 26 weeks of randomised treatment lies entirely below 0%; implying that the two sided p-value is less than 5%.

The multiple imputation procedure will be as follows:

For subjects in the liraglutide arm who are missing their week 26 HbA_{1c} measurement, measurements will be imputed using the subjects' baseline HbA_{1c} under a regression model based on the completers from the liraglutide placebo arm. Likewise, the same imputation model will be used for subjects in the liraglutide placebo arm with missing week 26 data. Multiple imputation of

Liraglutide		Date:	25 June 2018	Novo Nordisk
Trial ID: NN2211-3659	CONFIDENTIAL	Version:	2.0	
Statistical Analysis Plan	CONFIDENTIAL	Status:	Final	
EurdraCT No.: 2011-002605-29		Page:	14 of 25	

missing week 26 HbA $_{1c}$ data will be performed by utilizing the relationship between HbA $_{1c}$ measured at baseline and weeks 10 and 14 with that measured at week 26 in placebo patients. The following four regression models will be built from the liraglutide placebo completers group for this purpose:

- Model 1: Only baseline covariates (baseline HbA_{1c}, stratification group (gender*age group), concomitant diabetes treatment at baseline)
- Model 2: Baseline covariates and week 10 HbA_{1c} as covariates
- Model 3: Baseline covariates and week 14 HbA_{1c} as covariates
- Model 4: Baseline covariates, week 10 HbA_{1c}, and week 14 HbA_{1c} as covariates

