3.6.2 Supportive secondary endpoints

All supportive endpoints will be presented and analysed using FAS.

The supportive secondary endpoints will be analysed using the models as described for the confirmatory secondary analyses (see section 3.6.1).

In the analyses at week 52 the pattern mixture model is extended with the following models:

- Model 5: Baseline covariates and week 26 data of the endpoint as covariates
- Model 6: Baseline covariates and week 10, and week 26 data of the endpoint as covariates
- Model 7: Baseline covariates, week 14 and week 26 data of the endpoint as covariates
- Model 8: Baseline covariates, week 10, week 14 and week 26 data of the endpoint as covariates

Data at baseline, week 10, 14, 26 and 52 will be used in the pattern mixture model.

In the MMRM analysis for the supportive secondary endpoints data points at all visits, but excluding data collected after treatment discontinuation or initiation of rescue medication will be used.

The following dichotomous endpoints are defined:

At 26 and 52 weeks of treatment unless otherwise stated:

 $HbA_{1c} < 7.0\%$ (yes/no) at 52 weeks

 $HbA_{1c} \leq 6.5\%$ (yes/no)

HbA_{1c} <7.0% without severe or minor hypoglycaemic episodes (yes/no)

 $HbA_{1c} < 7.5\%$ (yes/no)

The dichotomous endpoints will be analysed by a logistic regression model. Effects in the model are treatment, stratification groups (gender*age group), and baseline HbA_{1c} as a covariate. The results

Liraglutide		Date:	25 June 2018	Novo Nordisk
Trial ID: NN2211-3659	CONFIDENTIAL	Version:	2.0	
Statistical Analysis Plan	CONFIDENTIAL	Status:	Final	
EurdraCT No.: 2011-002605-29		Page:	18 of 25	

will include the 95% confidence interval for the odds ratio (liraglutide over liraglutide placebo) and the p-value for test of no difference between the groups as part of the presentation.

Missing data at week 26 and week 52 will be imputed

- using the multiple imputation procedure as described above
- and in addition using imputations from the MMRM sensitivity analysis no. 4 of the primary endpoint.

The following continuous endpoints are defined:

Change from baseline at 26 and 52 weeks of treatment unless otherwise stated:

- HbA_{1c} at 52 weeks
- FPG at 52 weeks
- 7-point SMPG
 - mean 7-point SMPG, defined as the area under the profile (calculated using the trapezoidal method) divided by the measurement time

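### As written, the week-26 imputation for FPG and BMI SDS swaps only the baseline covariate, so placebo models still use interim HbA1c rather than the endpoint's own week-14 value

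*SAP*

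**What the plan says.** SAP 3.5 defines four regression models, built from placebo completers, to impute missing week-26 values. Model 1 has baseline covariates only. The others add interim HbA1c: "Model 2: Baseline covariates and week 10" HbA1c, Model 3 with week 14, and "Model 4: Baseline covariates, week 10 HbA_{1c}, and week 14 HbA_{1c} as covariates". A placebo subject's model is chosen by which HbA1c measurements that subject has. Liraglutide subjects always get Model 1.

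SAP 3.6.1 makes this pattern mixture model the primary analysis of the confirmatory secondary endpoints, "except that the baseline value of the analysed endpoint will be included instead of the baseline" HbA1c. The same single swap is repeated for FPG ("Baseline FPG will be included in the analyses instead of baseline" HbA1c) and for BMI SDS ("Baseline BMI SDS will be included in the analyses instead of baseline" HbA1c). Protocol 17.4.1 says the same. SAP 4.5, written to clarify what using the primary method means, does not mention the interim covariates.

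SAP 3.6.2 applies these models to the supportive endpoints and extends them at week 52 with Models 5 to 8, whose interim terms are values of the analysed endpoint. It adds: "Data at baseline, week 10, 14, 26 and 52 will be used in the pattern mixture model".

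On the schedule, Protocol 8.1.5 states: "Subjects must attend the clinic in a fasting state for Visits 1, 7, 13, 17, 22 and 25 blood sampling". Protocol 8.6.1 lists "Height (safety endpoint) (Visits 1, 7, 13, 17, 25, 27 and 28". Visit 12 is week 10 and Visit 13 is week 14. SAP 3.6.1 also plans an MMRM of both endpoints over all visits, without data collected after treatment discontinuation or rescue.

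**The concern.** FPG is second and BMI SDS fourth in the testing hierarchy, so the imputation behind each feeds a confirmatory p-value. With only the baseline swapped, a placebo child's missing week-26 BMI SDS is predicted from baseline BMI SDS and interim HbA1c, although a week-14 BMI SDS is available. The week-14 value of the same measure would be expected to predict better.

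For FPG there is also a possible bias. Central-laboratory FPG above the limit, once confirmed, leads to rescue, and persistence after rescue leads to withdrawal (Protocol 6.5 and 6.6). Data from withdrawn subjects count only if taken within 5 days of a planned visit (SAP 3.2), so some of these children will have no week-26 value. Visit 13 gives the only scheduled laboratory FPG between baseline and week 26. Leaving it out of the imputation omits the measured variable closest to that route to missingness.

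**Working it through.** **The plan's own figures.** The plan gives no figure on this point. Its sample size rests on HbA1c alone: a difference of 0.9 × (1 − 0.22) = 0.702 with SD 1.2, two-sided 5% and 80% power gives 47 per arm with the noncentral t distribution, as stated. Nothing below changes it.

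**The two readings against the schedule.**

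| | Interim HbA1c (literal 3.5 + 3.6.1) | Endpoint's own interim value (suggested by 3.6.2) |
|---|---|---|
| Week-10 input | HbA1c at Visit 12: yes | FPG: no. BMI SDS: weight yes, height no, and no rule for carrying height forward |
| Week-14 input | HbA1c at Visit 13: yes | FPG and height at Visit 13: yes |
| Models that can be fitted at week 26 | 1 to 4 | 1 and 3 only |
| Selection rule as written | Fits | Does not fit: a child with both interim HbA1c values is sent to Model 4, which has no input |

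At week 52, Models 6 and 8 need a week-10 value of the endpoint and fail in the same way for FPG and BMI SDS. Neither reading is complete as written.

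**Precision (illustration).** Let *m* be the fraction of placebo subjects missing at week 26, and *r* the correlation, given baseline, between the interim predictor and the week-26 value. The documents give no *r*. I assume 0.2–0.4 for interim HbA1c and 0.6–0.8 for the own week-14 value. I take *m* = 0.2 and 0.4; the upper value is the approximate placebo withdrawal in the adult trial cited in Protocol 17.1.

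If every leaver has a week-14 value, the SE of the placebo mean relative to complete data is √[1 + (m/(1−m))(1−r²)]:
- m = 0.2: 1.100–1.114 with HbA1c, 1.044–1.077 with the own value. Ratio 1.100/1.077 = 1.02 to 1.114/1.044 = 1.07.
- m = 0.4: 1.249–1.281 against 1.114–1.194. Ratio 1.249/1.194 = 1.05 to 1.281/1.114 = 1.15.

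This is an upper bound, because some children leave before week 14. If only a fraction *a* of the arm is both missing at week 26 and has a week-14 value, and c = 1 − m, the variance factor is 1/c − r²·a(2−c−a)/c. With half the leavers having a week-14 value:
- m = 0.2, a = 0.1, c = 0.8: factor 1.25 − 0.1375r². SE 1.108–1.116 against 1.078–1.096; ratio 1.01 to 1.04.
- m = 0.4, a = 0.2, c = 0.6: factor 1.667 − 0.4r². SE 1.266–1.285 against 1.188–1.234; ratio 1.03 to 1.08.

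These ratios are for the placebo mean. The change in the SE of the treatment difference is smaller, because the liraglutide arm uses Model 1 either way.

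**Bias in placebo FPG (illustration).** Understatement = fraction leaving × amount by which their week-14 FPG exceeds what the model predicts × slope of week-26 on week-14 FPG. With assumed inputs of 10–22%, 1–2 mmol/L and 0.4–0.6:
- low end: 0.10 × 1 × 0.4 = 0.04 mmol/L
- high end: 0.22 × 2 × 0.6 = 0.26 mmol/L

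A large-sample simulation agrees in direction. It assumed dropout log-odds rising by 1 per SD of week-14 FPG, a week-14 to week-26 correlation of 0.6–0.8, a correlation of 0.3–0.7 between HbA1c and FPG at week 14, and a week-14 value for everyone. Imputing from HbA1c understated the placebo mean by 0.06–0.13 SD at 20% missing and 0.11–0.24 SD at 40%. Imputing from the own week-14 value gave about 0. Leavers without a week-14 value would leave some bias under either approach.

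**The case against.** The strongest reply is that the baseline-swap sentence is shorthand. The primary method predicts an endpoint from its own earlier values, and using the same method for FPG should mean the same. SAP 3.6.2 supports this: it extends the same model family with terms in the analysed endpoint, and it would be odd for Model 7 to use week-14 FPG while Model 3 uses week-14 HbA1c. If model choice then follows available data, FPG and BMI SDS fall to Models 1 and 3, which is what the fix asks for.

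This stands as evidence of probable intent, so a reader should not infer that the plan settles on HbA1c. It does not close the gap. Three statements in SAP 3.6.1 and one in the protocol name only the baseline, the selection rule is tied to HbA1c availability, and 3.6.2 says week-10 data will be used where none are scheduled. Two careful programmers could produce different confirmatory p-values.

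A reader might also infer that the child's own week-14 value is used nowhere. That is wrong: the additional MMRM uses on-treatment, pre-rescue week-14 values of both endpoints. But it is not the primary analysis, and it leaves out data after discontinuation or rescue.

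Finally, the size of the bias rests on assumptions. FPG-driven withdrawal occurs only after rescue has failed, rescued subjects stay in the trial with their data counted, and the documents do not say how many would leave this way.

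**Conclusion.** The point holds for the week-26 multiple imputation of FPG and BMI SDS as literally written, and only for placebo subjects who miss week 26 but have interim values. The cost is modest: about 1–8% on the SE of the placebo mean if half the leavers have a week-14 value, and less on the treatment difference. For FPG, the placebo mean may be understated by a few hundredths to about a quarter of a mmol/L. All of these figures depend on assumed correlations, dropout fractions and deviations.

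A reader might infer a risk of a false claim for liraglutide. The documents do not support that: an understated placebo FPG shrinks the treatment difference. The harm is to pre-specification, accuracy and power for two tests in the hierarchy. The primary endpoint, the HbA1c <7.0% endpoint, the liraglutide arm's Model 1, N and alpha are unaffected. The change is worth making because it costs almost nothing.

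**What to change.** In SAP 3.6.1, state that for FPG and BMI SDS only Models 1 and 3 apply, that the Model 3 covariate is the endpoint's own week-14 value (interim HbA1c may be kept as an auxiliary), and that a placebo subject's model is selected by availability of that endpoint's data. In SAP 3.6.2, drop the models with a week-10 term (2, 4, 6 and 8) for endpoints not measured at week 10. The liraglutide arm stays on Model 1.

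This takes a few sentences, no new data and no change to the sample size. It should be settled before database lock and release of the randomisation code, the point that SAP 1.2 sets for finalising the plan. The downside is that placebo subjects with no week-14 value of the endpoint, such as those who leave between weeks 10 and 14, fall back to Model 1.

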3.6.2 Supportive secondary endpoints

All supportive endpoints will be presented and analysed using FAS.

The supportive secondary endpoints will be analysed using the models as described for the confirmatory secondary analyses (see section 3.6.1).

In the analyses at week 52 the pattern mixture model is extended with the following models:

- Model 5: Baseline covariates and week 26 data of the endpoint as covariates
- Model 6: Baseline covariates and week 10, and week 26 data of the endpoint as covariates
- Model 7: Baseline covariates, week 14 and week 26 data of the endpoint as covariates
- Model 8: Baseline covariates, week 10, week 14 and week 26 data of the endpoint as covariates

Data at baseline, week 10, 14, 26 and 52 will be used in the pattern mixture model.

In the MMRM analysis for the supportive secondary endpoints data points at all visits, but excluding data collected after treatment discontinuation or initiation of rescue medication will be used.

The following dichotomous endpoints are defined:

At 26 and 52 weeks of treatment unless otherwise stated:

 $HbA_{1c} < 7.0\%$ (yes/no) at 52 weeks

 $HbA_{1c} \leq 6.5\%$ (yes/no)

HbA_{1c} <7.0% without severe or minor hypoglycaemic episodes (yes/no)

 $HbA_{1c} < 7.5\%$ (yes/no)

The dichotomous endpoints will be analysed by a logistic regression model. Effects in the model are treatment, stratification groups (gender*age group), and baseline HbA_{1c} as a covariate. The results

Liraglutide		Date:	25 June 2018	Novo Nordisk
Trial ID: NN2211-3659	CONFIDENTIAL	Version:	2.0	
Statistical Analysis Plan	CONFIDENTIAL	Status:	Final	
EurdraCT No.: 2011-002605-29		Page:	18 of 25	

will include the 95% confidence interval for the odds ratio (liraglutide over liraglutide placebo) and the p-value for test of no difference between the groups as part of the presentation.

Missing data at week 26 and week 52 will be imputed

- using the multiple imputation procedure as described above
- and in addition using imputations from the MMRM sensitivity analysis no. 4 of the primary endpoint.

The following continuous endpoints are defined:

Change from baseline at 26 and 52 weeks of treatment unless otherwise stated:

- HbA_{1c} at 52 weeks
- FPG at 52 weeks
- 7-point SMPG
 - mean 7-point SMPG, defined as the area under the profile (calculated using the trapezoidal method) divided by the measurement time
 - post-prandial increments after breakfast, lunch and dinner (from before meal to 90 min after breakfast, lunch and dinner)
 - mean post-prandial increment for all meals (breakfast, lunch, and dinner)
- Fasting insulin, fasting pro-insulin, pro-insulin to insulin ratio, fasting glucagon, fasting C-peptide, and homeostasis model assessment (HOMA-B and HOMA-IR). The values will be logarithmically transformed before analysis, and the actual values will be modelled instead of change from baseline.
- Fasting lipid profile (total cholesterol, LDL cholesterol, VLDL cholesterol, HDL cholesterol, triglycerides and free fatty acids. The values will be logarithmically transformed before analysis, and the actual values will be modelled instead of change from baseline.
- Body weight
- Waist circumference
- BMI
- BMI SDS at 52 weeks
- BMI percentile (age and gender adjusted)
- Systolic and diastolic blood pressure

Throughout the trial:

• Basal insulin dose

For calculation of BMI SDS please refer to section 3.6.1 above.

BMI percentile (age and gender adjusted) is the result of the cumulative normal distribution function based on the respective Z-value (SDS value).

Liraglutide
Trial ID: NN2211-3659
Statistical Analysis Plan
EurdraCT No.: 2011-002605-29

Date: 25 June 2018 Version: 2.0
Status: Final
Page: 19 of 25

The continuous endpoints described above will be analysed with a similar method as for the primary endpoint (detailed above), except for change in basal insulin dose that will only be presented by descriptive statistics. The BMI percentile will also only be summarised (descriptive statistics) as it is uniquely determined from the BMI SDS. The post prandial increments after breakfast, lunch, and dinner will also only be presented by descriptive statistics, whereas the mean post-prandial increment will be analysed as the other endpoints.

If data has been log transformed, the ratio to baseline and treatment ratio will be considered instead of the change from baseline and treatment difference.

